6 For adults, **Table 2** (and **Attachment 3b**) provide the sample size calculations for several health outcomes 7 of interest assuming a type 1 (" α error") of .05 and type 2 error (" β error) of .20. In this exposure based 8 study we assume an appropriate coverage of range of exposures that will enable 9 stratification/categorization to tertiles or quartiles of exposure. Per stratum estimates of needed sample 10 size (e.g. first vs. fourth quartile) have been calculated based on different measures of association such as 11 odds ratios or detected mean difference.

12 The proposed sample size of 6,000 adults (equally of both sexes) is large enough to effectively evaluate 13 many of the health outcomes identified in the Pease Feasibility Assessment literature review. For example, for outcomes like elevated lipids levels (cholesterol) or uric acid, the range of 229 to 660 14 15 participants per stratum (i.e. quartile) or 200 to 550 per stratum, respectively, given observed differences would be needed. That would translate to overall sample size of about 800 to 2,600 participants being 16 sufficient to detect differences at the specified level of precision and power (Steenland, 2009, 2010; Fisher 17 18 2013; Shankar 2011). Similar sample sizes would also be required to compare other common health 19 outcomes such as cardiovascular disease (Shankar 2012). Larger samples sizes would be needed for liver 20 function or osteoarthritis, with a total sample in the range of 3,000 to 4,000 subjects (Uhl 2013; Gallo 21 2012; Steenland 2010).

22 For thyroid disease and thyroid function, a total sample size of 6,000 may be sufficient although probably 23 not optimal. However, NHANES studies of thyroid function and thyroid disease obtained statistically 24 significant findings with total sample sizes considerably less than 6,000 (Melzer 2010; Wen 2013). 25 NHANES studies of liver function also obtained statistically significant findings with total sample sizes 26 considerably less than 6,000 (Gleason 2015; n=4333). For biomarkers of immune function (e.g., immunoglobulins, C-reactive protein and cytokines) and fatty liver disease, there was insufficient 27 28 information to calculate sample sizes. However, a total sample size of 6,000 should be sufficient to 29 evaluate these biomarkers as we assumed similar endpoint differences of those outcomes.

For ulcerative colitis, a sample size of 6,000 might be sufficient if the effect size in the C8 study (i.e.,

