 OR=3.05) was consistent for PFOA serum levels considerably lower than those in the C8 study. For more

- 1 modest effect sizes (e.g., ORs < 2.75), a total sample size of 6,000 would not be adequate to evaluate
- 2 associations with ulcerative colitis.
- 3 In addition, several epidemiological studies of adults exposed to PFAS that reported robust statistical
- 4 associations with these health outcomes had smaller sample sizes than the one proposed for the Multi-
- 5 site Study, e.g., NHANES studies (Nelson 2010, Wen 2013), a C8 longitudinal study (Fitz-Simon 2013), a C8
- 6 immune study (Looker 2014), and studies in China (Fu 2014) and Korea (Ji 2012).
- 7 In summary, a total sample size of ≥6,000 in multi-site study should be sufficient to evaluate a broad range
- 8 of biomarkers and outcomes such as lipids (and hypercholesterolemia), uric acid (and hyperuricemia),
- 9 cardiovascular disease, osteoarthritis, immune biomarkers and biomarkers for fatty liver disease. It also
- 10 may be sufficient to evaluate thyroid disease, thyroid function and liver function.
- 11 **Table 2.** Sample size estimations for selected health-related endpoints in Adult Study.

Health-related Endpoint	Relevant Study	Observed Effect Size	Assumptions	Sample Size/Stratum α error = .05 β error = .20
Total Cholesterol (mg/dL)	Steenland 2009, C8 46,294 aged ≥18 yrs	PFOS, mean serum level = 19.6 μg/L, 10 th vs 1 st decile:+11 mg/dL	SD=41.9	228/stratum
High cholesterol		4 th vs 1 st quartile, OR=1.51	Prevalence=15%	660/stratum
High Cholesterol	Fisher 2013, Canada	PFHxS, mean serum level = 2.2 μ g/L, 4 th vs 1 st quartile, OR=1.57	Prevalence=44%	290/stratum
Cardiovascular disease	Shankar 2012, NHANES 1,216 aged ≥40 years	PFOA mean serum level = 4.2 μ g/L, 4 th vs 1 st quartile: OR=2.01	Prevalence = 13%	250/stratum
Uric Acid	Steenland 2010, C8 53,458 aged ≥20 yrs	PFOS mean serum level = 20.2 μg/L, 10 th vs 1 st decile: +0.22 mg/dL	SD=1.55	780/stratum
		Hyperuricemia, 5 th vs 1 st quintile: OR=1.26	Prevalence:24%	1,525/stratum
Uric Acid	Shankar 2011, NHANES 3,883 aged ≥20 yrs	PFOA mean serum level = 3.5 μg/L, 4 th vs 1 st quartile: +0.44 mg/dL	SD = 2.5	507/stratum
		Hyperuricemia, 4 th vs 1 st quartile: OR=1.97	Prevalence: 19.2%	200/stratum
		PFOS mean serum level = 17.9 μg/L		550/stratum

		Hyperuricemia, 4 th vs 1 st quartile: OR=1.5		

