Liver function Elevated ALT	Gallo 2012, C8 46,452 aged ≥18 yrs	PFOA and PFOS mean serum levels were 28 μg/L and 20.3 μg/L, respectively. PFOA: OR=1.54 PFOS: OR=1.25	Prevalence = 11.2%	725/stratum 2,917/stratum
Liver function ALT (μΙU/mL)	Gallo 2012, C8 46,452 aged ≥18 yrs	The top quintile of serum PFOS in the Pease population was 15 μ g/L. This would approximately correspond to a mean difference in ALT of +1.8 μ IU/mL	SD=1.47	1,958/stratum
Liver function Elevated ALT	Gleason 2015, NHANES 4,333 aged ≥12 yrs	PFHxS mean serum level = 1.8 μg/L. 4 th vs 1 st quartile: OR=1.37	Assumed similar prevalence as in the C8 study	1,570/stratum
Thyroid disease	Melzer 2010, NHANES 1,900 men, aged ≥20 yrs 2,066 women, aged ≥20 yrs	PFOA, mean serum level=3.5 μg/L, 4 th vs 1 st quartile: Thyroid disease ever: Women, OR=1.64 Men, OR=1.58 Thyroid disease with current meds Women OR=1.86	Prevalences: 16.18% 3.06%	410/stratum 2,035/stratum
		Men, OR=1.89	1.88%	1,575/stratum
Subclinical hypothyroidism	Wen 2013, NHANES 672 males aged ≥20 yrs 509 females aged ≥20 yrs	PFHxS mean serum level averaged about 2 μg/L. Unit increase in Ln(PFHxS): Women, OR=3.10 Men, OR=1.57	Prevalences: 1.6% 2.2%	475/stratum 2,918/stratum
Osto o utbuitio	Jan es 2011 - C0	00-142	Drevelopes 7 C0/	1 500 / atmatume
Osteoartmitis	49,432 aged >20 vrs	0n-1.42	FIEVAIENCE=7.0%	1,580/stratum
Osteoarthritis	Uhl 2013, NHANES 4,102 aged 20-84	PFOA mean serum level = 5.4 μ g/L , 4 th vs 1 st quartile: OR=1.55 PFOS mean serum level = 24.6 μ g/L , 4 th vs 1 st quartile: OR=1.77	Assumed similar prevalence as in the C8 study	978/stratum 550/stratum
		$\mu_{\text{B}/\text{L}}, 4^{}$ vs 1 quartile: OK=1.77		
Ulcerative colitis	Steenland 2013, C8 28,541 community and 3,713 worker cohorts	OR=3.05	Prevalence=0.5%	1,480/stratum

1 For rare health outcomes such ulcerative colitis, other autoimmune diseases, or cancer the sample size of

2 6,000 adults is too small to detect reasonably expected increases in the ORs.

3 It should be noted that the number of PFAS epidemiological studies available for each of the outcomes is

4 limited, and the actual differences in clinical and research parameters may be quite different in the Multi-

site study than have been observed in the PFAS literature. Sample size estimates provide guidance and
 may be useful for planning purposes but should be interpreted with caution, especially given the limited
 nature of the PFAS literature.

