Attachment 3 – Justification for Sample Size Calculations (Supporting information)

- Attachment 3a Child Sample Size Calculations
- Attachment 3b Adult Sample Size Calculations

Sample size calculations were conducted using OpenEpi Version 3.03 (Dean AG, Sullivan KM, Soe MM. OpenEpi: Open Source Epidemiologic Statistics for Public Health, www.OpenEpi.com, updated 2014/09/22). For some health-related endpoints, calculations could not be conducted because of a lack of information in the studies on the parameters needed to make the calculations.

Sample size calculation for mean difference:

$$n_{1} = \frac{(\sigma_{1}^{2} + \sigma_{2}^{2} / \kappa)(z_{1-\alpha/2} + z_{1-\beta})^{2}}{\Delta^{2}}$$
$$n_{2} = \frac{(\kappa * \sigma_{1}^{2} + \sigma_{2}^{2})(z_{1-\alpha/2} + z_{1-\beta})^{2}}{\Delta^{2}}$$

The notation for the formulae are:

$$n_1 = \text{sample size of Group 1}$$

 $n_2 = \text{sample size of Group 2}$
 $\sigma_1 = \text{standard deviation of Group 1}$
 $\sigma_2 = \text{standard deviation of Group 2}$
 $\Delta = \text{ difference in group means}$
 $\kappa = \text{ratio} = n_2/n_1$
 $Z_{1-\alpha/2} = \text{two-sided Z value (eg. Z=1.96 for 95\% confidence interval).}$
 $Z_{1-\beta} = \text{power}$

Where N_2/N_1 is the ratio of the two sample sizes. Then N_2 is simply this ratio multiplied by N_1 . For a type 1 error (or α error) of .05, the $Z_{1-\alpha/2}$ value is 1.96. This calculation is for a two-tailed hypothesis test and equivalent to using a 95% confidence interval to determine statistical significance. For a one-tail test with α =.05, the $Z_{1-\alpha/2}$ in the above equation is replaced by $Z_{1-\alpha}$ and its value is 1.65, equivalent to using a 90% confidence interval to determine statistical significance. For 80% confidence interval to determine statistical significance. The $Z_{1-\beta}$ in the above equation is the Z value for the selected power. For 80% power, $Z_{1-\beta} = 0.84$, for 90% power, $Z_{1-\beta} = 1.28$, and for 95% power, $Z_{1-\beta} = 1.65$. (See Rosner B. Fundamentals of Biostatistics, 7th Edition, equation 8.27, p. 302).

Fleiss JL. Statistical Methods for Rates and Proportions. John Wiley & Sons, 1981.

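### Table 2 sizes subclinical hypothyroidism with odds ratios per one-unit increase in ln(PFHxS) entered as if they were odds ratios between exposure strata; at the NHANES exposure spread the men's 2,918 per stratum is about 3.4 to 5.5 times too large

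*Protocol*

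**What the plan says.** Section 3.3.2 of the protocol introduces the Table 2 figures as per-stratum sizes and gives the intended contrast by example: "size (e.g. first vs. fourth quartile) have been calculated based on different measures of association". The column heading sets "α error = .05 β error = .20", and Attachment 3 says of its formula for means: "This calculation is for a two-tailed hypothesis test and equivalent to using a 95% confidence interval to determine statistical significance".

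The subclinical hypothyroidism row states its effect as "Unit increase in Ln(PFHxS): Women, OR=3.10 Men, OR=1.57", its prevalences as "Prevalences: 1.6% 2.2"% (women, then men) and its sizes as "475/stratum 2,918/stratum". Neither Table 2 nor Attachment 3b describes any conversion from the per-unit scale to a contrast between strata for this row.

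Attachment 3b does convert elsewhere. In its adult TSH example a coefficient per unit of ln(PFOS), 0.129, is multiplied by ln 15 = 2.71 before the size is calculated. The TSH and TT4 examples that follow it multiply per-unit coefficients by 15 ng/mL (PFOS) and 9 ng/mL (PFHxS).

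On numbers available, the text says: "The proposed sample size of 6,000 adults (equally of both sexes) is large enough". On this group of outcomes it concludes: "For thyroid disease and thyroid function, a total sample size of 6,000 may be sufficient although probably" not optimal.

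**The concern.** An odds ratio per unit of ln(PFHxS) compares two people whose serum levels differ 2.7-fold. A comparison of the top and bottom quartiles spans whatever difference in ln(PFHxS) separates those quartiles, and the per-unit odds ratio must be raised to that power before it is used as a stratum odds ratio. If the quartiles lie clearly more than one ln-unit apart, the unconverted figure understates the stratum effect and overstates the size needed.

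The men's row is where this matters. At 2,918 per stratum, quartiles would need 4 × 2,918 = 11,672 men, when 3,000 are planned. A reader would take the comparison to be out of reach.

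**Working it through.** **Inputs.** Two-sided alpha 0.05 and power 0.80 (Table 2 heading; the two-sided statement is in Attachment 3). Women: OR 3.10 per ln-unit, prevalence 1.6%. Men: OR 1.57 per ln-unit, prevalence 2.2%. Available: 6,000 adults, half of each sex, so 3,000 men, or 750 per quartile. Spread of ln(PFHxS): the documents give none for this study or for the cited study. The only adult figures are the NHANES 2013-2014 50th and 95th percentiles for ages 20+ in Attachment 2, 1.40 and 5.50 µg/L. Lognormality is my assumption.

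**Step 1. Reproduce the printed sizes.** Take p2 = OR·p1 / (1 − p1 + OR·p1), then the usual two-proportion formula with pooled variance under the null and no continuity correction.

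- Women: p1 = 0.016, p2 = 0.0480, n = 474 (printed 475).
- Men: p1 = 0.022, p2 = 0.0341, n = 2,917 (printed 2,918).

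The averaged-variance form gives 476 and 2,918. A continuity correction gives 535 and 3,080, and a one-sided test 374 and 2,298; neither fits. So the per-unit odds ratios were entered directly, with the stated prevalence as that of the reference stratum. On that basis the men's power at 750 per quartile is 29%.

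**Step 2. Exposure contrast.** SD of ln = ln(5.50/1.40)/1.645 = 1.368/1.645 = 0.83. Between the top and bottom quartiles of a normal variable:

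- difference in stratum means = 2 × φ(0.674)/0.25 × SD = 2.54 × 0.83 = 2.11 ln-units;
- difference in stratum medians = 2 × 1.150 × 0.83 = 1.91 ln-units.

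**Step 3. Men, converted.**

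- 2.2% as reference prevalence: stratum OR = 1.57^1.91 = 2.37 to 1.57^2.11 = 2.60, giving n = 669 to 529 per quartile and power at 750 of 84% to 92%.
- 2.2% as overall prevalence: a logistic slope over the assumed distribution puts the bottom quartile at 1.31% and the top at 3.33%, giving n = 868 and power 74%.

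Against 2,918 these are ratios of 2,918/868 = 3.4 to 2,918/529 = 5.5.

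**Step 4. Dependence on the spread (men, first against fourth quartile).**

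| SD of ln(PFHxS) | n, 2.2% as reference | n, 2.2% overall | Power at 750 |
|---|---|---|---|
| 0.5 | 1,712 to 2,140 | 2,286 | 36% to 46% |
| 0.7 | 794 to 1,000 | 1,199 | 60% to 78% |
| 0.83 | 529 to 669 | 868 | 74% to 92% |
| 1.0 | 339 to 432 | 621 | 87% to 99% |

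With 2.2% as reference prevalence, 750 per quartile gives 80% power once the quartiles differ by about 1.82 ln-units (OR about 2.28).

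**Step 5. Cross-check on the scale of the estimate.** For a test of slope, total n = (1.96 + 0.84)² / [p(1 − p)(ln OR × SD)²]. With p = 0.022, ln 1.57 = 0.451 and SD 0.83, this gives about 2,590 men, against 3,000 planned (power about 85%). At SD 0.5 it gives 7,172, so the same dependence on spread appears.

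**Step 6. Women.** At SD 0.83 the conversion gives 65 to 87 per quartile with 1.6% as reference prevalence, or 267 with 1.6% overall. At SD 0.5 on the overall reading it gives 574, slightly above the printed 475. All of these are below 750.

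**The case against.** The strongest reply is that the consequence is small and the replacement figure uncertain. The spread of 0.83 comes from two general-population percentiles, both sexes pooled. At SD 0.5 the men's comparison remains well underpowered. A reader might infer that it is in truth adequate; the documents do not support that without a stated spread, and even at 0.83 the overall-prevalence reading needs 868 against 750. The aim in section 1.1.3 of selecting sites with a wide range of exposure makes a narrow spread less likely, but it is not quantified.

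A reader might also infer that one ln-unit cannot be the right contrast for any split. That goes too far. Section 3.3 and Attachment 3 allow tertiles, and at SD 0.83 the middle and bottom tertile means differ by about 0.91 ln-units. The mismatch concerns top-against-bottom comparisons, which is the example section 3.3.2 gives.

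Nor does the row alone produce the cautious thyroid sentence. Table 2 gives 2,035 and 1,575 per stratum for thyroid disease in men, and Attachment 3b gives 4,716 per group for TT4 with PFHxS. That sentence survives the correction.

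For women, a converted figure as low as 65 would be worse than the printed one: 65 × 0.016 is about one expected case in the reference stratum, where the normal approximation is unreliable.

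Finally, section 3.3.2 warns that its size estimates call for caution. That covers uncertain effect sizes, not an effect entered on the wrong scale. So these objections limit the size and reach of the point but leave the scale error in place.

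**Conclusion.** The scale error is established: both printed sizes follow from using a per-ln-unit odds ratio as a stratum odds ratio, contrary to the contrast described in section 3.3.2 and to the practice in Attachment 3b. The printed sizes are too large if the top and bottom quartiles differ by clearly more than one ln-unit.

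How much too large is conditional. Under lognormal PFHxS at the NHANES spread, with a log-linear effect over the whole range, men need about 530 to 870 per quartile rather than 2,918, and power at 750 is 74% to 92% rather than 29%. At SD 0.5 the need is about 1,710 to 2,290 with 36% to 46% power; at SD 1.0 it is about 340 to 620. The conclusion for women does not change, and the planned total of 6,000 is not called into question.

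**What to change.** Recompute the row in one of two ways. Either raise the per-ln-unit odds ratio to a stated first-to-fourth-quartile difference in ln(PFHxS), showing the assumed spread, a range around it, and whether the prevalence is that of the reference stratum or of the whole sample. Or size the row as a test of slope on ln(PFHxS), the scale on which the effect was estimated. Do not print an extrapolated women's size as low as 65.

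Leave the general thyroid sentence in 3.3.2 as it is. At most add that men's subclinical hypothyroidism is less far out of reach than 2,918 suggests if the exposure spread is at least that of NHANES.

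The cost is one recalculated row and a note of its assumptions, with no change to design or enrolment.

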7 3.6.2.3 Adult Consent

Before any data collection can begin in the adult study, trained study staff will review the hardcopy Adult
Consent Form with the interested recruit (Attachment 7b4). The study staff will explain the purpose of
the study and obtain written informed consent for the completion of a questionnaire, the collection of a
new fasting blood specimen, the storage of this blood specimen for future analyses, access to medical
records (Attachment 7b5), and permission to contact the participant in the future for a possible study .
After signing the consent form, the adult will become a study participant.

14

15 3.6.2.4 Risks and Benefits

As further described in **Section 3.8.1**, the recipient will inform the participant that his or her participation is protected by a Certificate of Confidentiality under Section 301(d) of the Public Health Service Act as amended by Section 2012 of the 21st Century Cures Act. The recipient will further inform the participant that access to identifiable occupational history, private medical records, and to school records are protected from certain disclosures under Section 301(d) of the PHSA.

The risks of participation in this study are minimal (defined in 45 CFR 46.110). In-home urine collections are minimal risk. This study plans for a one-time 23-ml (5 teaspoons) volume of fasting blood collected from the child and a one-time 33-ml volume of fasting blood collected from the adult. These amounts of blood are the minimum necessary to conduct analyses for PFAS and the effect biomarkers (**Attachment 2**). After the blood draw, the participant will be offered a small snack, thereby allowing monitoring of adverse events due to phlebotomy.

Participants in this study will not receive any direct benefit from taking part in this research. Their taking part in this research will provide the scientific community and the public a better understanding of how exposures to PFAS-contaminated drinking water may affect human health. Each adult participant and the parent of the child participant will receive the results of the analyses of serum PFAS levels and effect
- 1 biomarkers. They will receive the results of their urine PFAS and effect biomarker levels, if ATSDR identifies
- 2 meaningful urinary analyses to perform.

3 **3.6.3 Update Contact Information and Medication List**

The adult participant and the parent of the child participant will be asked to verify and update his or her

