Fasting Blood Specimen and First Morning Urine Void Collection: Participants will transport their urine sample to study office for collection. Trained staff will collect and record the urine specimen intake (Attachment 14). The blood collection procedure consists of administering and recording responses to a blood draw screening questionnaire for conditions that exclude the participant from the blood draw (hemophilia, skin condition, or chemotherapy in the past four weeks, and pregnancy), ask about having diabetes, taking blood thinning medications, participant's weight, and fasting status (Attachment 14). Next, phlebotomists will draw 23-ml (0.8 ounces or about 5 teaspoons) of blood from the child participant and 33-ml (1.1 ounces or about 7 teaspoons) of blood from the adult participant using standard venipuncture techniques (Attachment 12) and record the outcome (Attachment 14). If a person is unable to provide the desired volume of blood, a smaller amount can be drawn and documented. Trained study staff will record the phlebotomy and urine collection result on the Blood Draw and Urine Collection Form (Attachment 14).

Common adverse events from blood draws include bruising, bleeding, and fainting. No serious adverse events are anticipated in drawing these volumes of blood. Fasting diabetic participants who use insulin will receive priority appointments for their blood draw. Light snacks will be provided following blood collection. While each participant will be asked to provide a fasting sample, it is recognized that some may not be able to fast. Variations in lipids levels due to fasting will affect PFAS compounds measurements to a lesser extent as PFAS in serum are bound to proteins not the lipid fraction. . In the C8 Science Panel studies, about 25% of participants fasted – but they were not asked to do so (Frisbee 2009).

Phlebotomists will extract serum, and label and prepare the serum and urine specimens for secure storage
 and transport from the study office to the CDC NCEH laboratory in Atlanta, GA (Attachment 12).

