				Luteal: 1.8-5.1 IU	J/L
				Postmenopausal	: 16.7-113.6 IU/L
Insulin-like growth factor (IGF-1)					
	Follicle stimulating hormone (FSH) Stage IV Stage V ADULTS Males: 10-57 nm Remales (non-pr Males? 4-6 years: < or =				

⁹ https://www.mayomedicallaboratories.com/test-catalog/Clinical+and+Interpretive/8670

Laboratory and Contact	tory and Analyte		Matrix	Volume	Reportable Range, Guidelines, Critical Values Reference ranges will be updated when commercial lab is selected.
Children and Adults		-		2	
Commercial	Immune Function				
Laboratory (to be determined)* Contact:	lg A, lg G, lg M, lg E		Serum	1 ml	
	Glycemic Parameters				
Commercial	Glycosylated hemoglobin (HbA1c)		Whole Blood EDTA	1 ml; plus 1 ml reserve	Diabetes Risk¹⁰ Normal: <5.7% Increased Risk Diabetes: 5.7-6.4% Diabetes: ≥6.5% (confirmation required)
Laboratory (to be	Glucose, fasting, 8-hour Insulin			0.5 ml	
determined)*				Glucose/	<17 μU/ml ⁸
contact:	Glutamate Decarboxylase -65 (Anti-GAD 65)		Serum	Insulin; 1 ml	Negative Antibody: DK≤33 ⁸ Positive Antibody: DK>33
	Thurseine Dheenhetere like Drotein Autoentihedies (Anti 142)			antibodie	Negative Antibody: DK<5 ⁸
	myrosine prosphatase-like protein Autoantibodies (Anti-IAZ)			S	Positive Antibody: DK≥5
Children Only					
Commercial Laboratory (to be determined)* Contact:	Antibodies to measles, mumps, rubella, tetanus, and diphtheria	Yes	Serum	1 ml	
		Serum - 9n Red Top 2	nl Whole Blood – 2 ml Urine – 16 ml x10 ml EDTA Lavender Top 3 ml		

Adults Only				
	Autoimmune Parameters	Yes	Serum	

¹⁰ American Diabetes Association. Standards of Medical Care in Diabetes - 2011. Diabetes Care. January 2011;34(Supplement 1):S11-S61 (subject to periodic update).

	Rheumatoid Factor (RF)				< 15 IU/mL ¹¹
Commercial Laboratory (to be determined)* Contact:	Antinuclear Antibody (ANA) screen			2 ml (for all)	< or =1.0 U (negative) ¹² 1.1-2.9 U (weakly positive) 3.0-5.9 U (positive) > or =6.0 U (strongly positive)
	Antinuclear Antibody (ANA) titer				
		ļ	Adult Total	Serum – 1 Red Top 3	L ml Whole Blood – 2 ml Urine – 16 ml x 10 ml EDTA Lavender Top 3 ml

 ¹¹ https://www.mayomedicallaboratories.com/test-catalog/Clinical+and+Interpretive/9060
 ¹² https://www.mayomedicallaboratories.com/test-catalog/Clinical+and+Interpretive/9026

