- Identify issues that must be addressed prior to starting future health studies at sites where exposures to PFAS-contaminated drinking water have occurred.

2. How was the drinking water at this site contaminated with PFAS?

The source of the PFAS contamination was the use of aqueous film-forming foam (AFFF), a fire suppressant agent, at the [insert site]. AFFF ingredients include PFAS. PFAS migrated from the soil into the ground water at the base and then to the [insert name(s)] supply well and the two other supply wells serving [insert site].

3. Who is eligible for the study?

Children aged 4-17 years and adults aged \geq 18 years are eligible for the study if they worked or attended childcare at the site, were exposed in utero or during breastfeeding, or lived in a home near the site that was served by a PFAS-contaminated private well.

Persons with occupational exposures to PFAS (e.g., firefighters who used or trained with AFFF) and children whose mothers were occupationally exposed to PFAS are not eligible for the study.

Eligible females who are pregnant may enroll; however, the federal regulations say that people in prison, including those under house arrest, cannot take part in this type of study.

4. What is required in order to participate in the study?

Each participant (or the parent of a child participant) must sign a consent form. The consent form describes the study procedures and risks and benefits of participation. The consent form will request permission to obtain a blood and urine sample. These samples will be analyzed for PFAS and for health indicators such as cholesterol levels, liver function, thyroid function and immune function. The participant's test results will be provided to the participant along with information on how to interpret the results. The consent form will also request that the participant (or parent of the child participant) complete a health and exposure questionnaire. The consent form will ask permission to obtain body measurements (blood pressure, weight, height, waist and hip circumference). The consent form will request permission to obtain the participant's medical records and the child participant's special education records (e.g., IEP evaluation report or 504 Plan). Finally, the consent form for children participants will request permission to administer behavioral tests to the child and obtain information from the parent concerning the child's behaviors.

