ATSDR estimates the average public reporting burden for this of instructions, searching existing data/information sources, gath the collection of information. An agency may not conduct or sp displays a currently valid OMB Control Number. Send commen including suggestions for reducing this burden to CDC/ATSDR I 30333; ATTN: PRA (0923-xxxx).	collection of information as 10 minutes per re ering and maintaining the data/information oonsor, and a person is not required to respo ts regarding this burden estimate or any oth nformation Collection Review Office, 1600 Cl	esponse, including the time for reviewing needed, and completing and reviewing and to a collection of information unless it er aspect of this collection of information, lifton Road NE, MS D-74, Atlanta, Georgia
Adult Study ID No.:	OR Child Study ID No.: _	
You were asked to collect a first morning v	oid urine sample when you got	up today.
1. Did you bring it today?		🗆 Yes 🗆 No
1a. [IF NO] Can you give us a sample	e now?	🗌 Yes 🗌 No
2. Result of the urine collection (mark one)	Volume	
Complete	(at least 10-mL)	
Partial	2a. (mL)	
Unable to collect		
Before we can take [your/your child's] blo [you/your child] can provide a blood samp	od we need to ask you a few qu le.	estions on whether
3. [Do you/Does your child] have hemophilia?		🗆 Yes 🗖 No
4. [Have you/Has your child] received any c	hemotherapy in the last four we	eks? 🗌 Yes 🗌 No
5. [Do you/Does your child] have active som arm/shoulder that could prevent us from	es, disease, or other problem on n taking a blood sample*?	the 🗌 Yes 🗌 No
* This may include gauze dressings casts ed	ema naralysis tubes onen sores o	wounds withered arms or

* This may include gauze dressings, casts, edema, paralysis, tubes, open sores or wounds, withered arms or limbs missing, damaged, sclerosed or occluded veins, allergies to cleansing reagents, burned or scarred tissue, shunt or intravenous lines on both arms. Please check and review all with the participant.
[IF THE ADULT/PARENT OR GUARDIAN RESPONDED 'YES' TO ANY OF THE ABOVE QUESTIONS, THE PARTICIPANT SHOULD BE EXCLUDED FROM THE BLOOD DRAW. PLEASE SEE STUDY COORDINATOR IMMEDIATELY.

SENIOR SUPERVISING NURSE WILL MAKE THE DECISION WHETHER A PARTICIPANT WITH ANY TYPE OF SHOULDER LESIONS CAN SAFELY PROVIDE A BLOOD SAMPLE]

We also want to ask you a few more questions as a precaution.

5. [Are you/Is your child] on blood thinning medication?		🗆 Yes 🗆 No
7. Are you on diabetes medication or insulin?		🗆 Yes 🗌 No

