8. Tell me the last time you ate. Was it less than	n eight hours ago?	🗆 Yes 🗌 No
8a. [IF YES] How long ago did you eat?	: (hours and minutes)	
8b and what did you eat?	I	
[IF THE PARTICIPANT ANSWERED 'YES' TO ANY COORDINATOR AND SUPERVISING NURSE TO M	OF THE ABOVE QUESTIONS PLEASE SEE S IAKE SURE THEY CAN SAFELY PROVIDE BI	TUDY LOOD SAMPLE]
9. Result of the Blood Draw (mark one)	Volume	
□ Complete	(35-mL adults/25 ml children)	
Partial	7a. (mL)	
Unable to collect		
9a. Date: _ / / 9b. Tin	ne: _ : 🗆 AM 🗆 PM	
9c. Code Partial/Inability to Collect (circle one)		
Reason for partial or inability to collect blood:		
 Pregnant Medical (e.g. patient frail, weak, lost consciousness) Refused 		
4. Other (describe)		

NOTES: Care should be used in drawing blood from all subjects. Common adverse effects include bruising, bleeding, and fainting. Please ask all participants whether they prefer to lie down to have blood drawn.

Ask everyone if they tend to faint when giving blood. Suggest they sit down for five minutes after giving blood.

Fasting diabetic participants who use insulin will be given priority appointments for their blood draw.

Light snacks will be provided following blood collection.

See Protocol Attachment 14 (Manual of Operations) for further details on collecting blood samples.

[ON INVESTIGATORS INSTITUTION LETTERHEAD] [DATE]

[NAME OF PROVIDER] [ADDRESS] [CITY, STATE ZIP CODE]

Subject: Medical verification and records review for Multi-site PFAS Health Study

Dear [NAME OF PROVIDER]:

The Agency for Toxic Substances and Disease Registry (ATSDR) and [insert institution name] are conducting a research study of the health effects from exposure to per- and polyfluoroalkyl substances (PFAS) found in drinking water. We are working with the assistance of your local health department [insert name] and [name of all other partners]. ATSDR and research partners are conducting this research study with oversight from the CDC/ATSDR Institutional Review Board (IRB) under CDC Protocol No. xxxxxxx.

Under Section 8006 of the 2018 Consolidated Appropriations Act, Congress authorized ATSDR to study the impact that exposure to PFAS in drinking water might have on the health of affected citizens. This study will see if there is an increase of symptoms or illness related to these chemicals.

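### The blood draw form never asks about pregnancy, although section 3.6.4 lists pregnancy as a condition that excludes the draw

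*Protocol*

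**What the plan says.** Section 3.6.4 (Body and Clinical Measurements) describes the blood collection procedure as starting with a screening questionnaire whose answers are recorded, and cites Attachment 14 for it. The questionnaire is said to cover "conditions that exclude the participant from the blood draw (hemophilia, skin condition, or chemotherapy in the past four weeks, and pregnancy". It is also said to ask about diabetes, blood thinners, weight and fasting.

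The Blood Draw and Urine Collection Form is Attachment 14 in the list of attachments and is printed after Attachment 15a. It puts three questions before its stop rule: hemophilia, chemotherapy in the last four weeks, and sores or other problems of the arm or shoulder. If any answer is yes, "THE PARTICIPANT SHOULD BE EXCLUDED FROM THE BLOOD DRAW". Precautionary questions follow on blood thinners, diabetes medication and the last meal. Pregnancy appears once, in the 9c list of reasons for a partial or missed draw: "Pregnant Medical (e.g. patient frail, weak, lost consciousness) Refused".

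The eligibility criteria for adults (section 3.2.2) do not exclude pregnant women. The draft website flyer (Attachment 5f) says "Eligible females who are pregnant may enroll".

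On volume, section 3.6.2.4 plans a "one-time 33-ml volume of fasting blood collected from the adult" and 23 mL from the child, and section 3.6.4 repeats both figures. Item 9 of the form prints "35-mL adults/25 ml children" beside the box for a complete draw.

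**The concern.** Section 3.6.4 sets an exclusion for the individual participant and names the form that applies it, but the form does not collect the fact that the exclusion depends on. Its stop rule works only on the questions printed above it, and pregnancy is not one of them. A pregnant participant who does not raise the matter passes the screen, is drawn, and is recorded as a complete draw. She never reaches item 9c, so the form would not show the departure from the protocol afterwards either.

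What is at stake is a participant-protection rule and the record that it was followed. The biomarker and exposure models are not affected in any way that can be shown from the documents.

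The difference in blood volume is separate and minor. It leaves two figures in the plan for what counts as a full draw.

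**Working it through.** The main point is a comparison of texts; arithmetic enters only for scale and for the volume figures.

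**1. Section 3.6.4 against the form**

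| Condition in 3.6.4 | Asked before the stop rule? | Where on the form |
|---|---|---|
| Hemophilia | Yes | Item 3 |
| Chemotherapy, past four weeks | Yes | Item 4 |
| Skin condition | Yes | Item 5 (sores or arm/shoulder problem) |
| Pregnancy | No | Only as a 9c reason code |

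Three of the four listed conditions are asked. The precautionary items after the stop rule do not ask about pregnancy either.

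**2. Could a question have been lost from the text?** The printed item numbers run 1 to 5, then a second 5 (blood thinners), then 7, 8 and 9. Reading the second 5 as a misprinted 6 leaves no empty slot, and there is no sign of a redaction. That reading is an inference, but nothing on the page points to a missing item.

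**3. Does another step shown in the protocol ask first?**
- Eligibility screening script (Attachment 4): it asks about age, firefighting, industrial work and custody, not pregnancy.
- Reminder call (Attachment 8): it asks about diabetes medication only.
- Child questionnaires (Attachments 15 and 15a, items F10 and F11): they ask whether a daughter has ever been pregnant, with dates. The appointment tracking form (Attachment 9) leaves the order of draw and questionnaire to the coordinator, so the answer may come after the draw.
- Manual of Procedures (Attachment 12): a placeholder.
- Adult questionnaire and consent forms: not shown, so nothing is claimed about them.

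**4. Scale**
- Planned adults: "The proposed sample size of 6,000 adults (equally of both sexes"), hence 6,000 × 0.5 = 3,000 women.
- Share pregnant at the visit: not given in the documents; 1% to 3% is assumed.
- 3,000 × 0.01 = 30; 3,000 × 0.02 = 60; 3,000 × 0.03 = 90.

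This counts women who would reach the form without being asked. It does not count women who would in fact be drawn.

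**5. Volume**

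Attachment 2 plans two 10 mL red-top tubes per child and three per adult, plus one EDTA tube each ("EDTA Lavender Top 3 ml").
- Child: 2 × 10 + 3 = 23 mL. Adult: 3 × 10 + 3 = 33 mL. Both reproduce the figures in sections 3.6.2.4 and 3.6.4.
- Form, item 9: 25 − 23 = 2 mL too high for children, and 35 − 33 = 2 mL too high for adults.

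**The case against.** The strongest reply is that the gap lies on a printed form and may not be a gap in the study. Having a pregnancy code in 9c suggests that staff are expected to know a participant's status. The adult questionnaire takes reproductive and menstrual history at the same visit. The Manual of Procedures, which is to govern specimen collection, is not yet written. Section 3.6.4 also credits Attachment 14 with a question on weight, which is in fact recorded on Attachment 13, so an item assigned to one form can be collected on another. The flyer is marked as incomplete and still carries text from the Pease study, so it is weak evidence of enrollment policy. The 1% to 3% is assumed and is applied to all women of 18 and over, many of them past childbearing age.

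Part of this stands. The documents do not show that the study as a whole fails to screen for pregnancy, and the 30 to 90 is illustrative only. The flyer is not needed, because section 3.2.2 leaves pregnant women eligible in any case.

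The contradiction remains. A reason code completed after the draw collects nothing before it. No step that can be seen is guaranteed to ask about pregnancy before the draw. The weight item has a known home on another form, whereas none is shown for current pregnancy ahead of the needle.

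**Conclusion.** The concern holds. The form that section 3.6.4 names as the screen asks about three of the four conditions listed there, and the one it omits is pregnancy. As written it cannot enforce the exclusion, whatever the number of pregnant participants. On the assumed prevalence of 1% to 3% among 3,000 planned women, 30 to 90 would meet the gap.

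The conclusion is limited to the form as printed. It does not extend to the unwritten manual or to the consent forms and adult questionnaire, which are not shown. It should be put right before use, but it does not threaten the validity of the study.

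The 2 mL discrepancy in each age group is real but clerical. A true shortfall would not be lost, because the form records the volume of a partial draw and the reason for it.

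**What to change.** Add to Attachment 14, above the exclusion instruction, a yes/no question on whether the participant (or the child) is currently pregnant, and record the answer. Pregnant women can still enroll and complete the rest of the visit; only the draw is barred, as section 3.6.4 already states. Keep the 9c code, which would then follow from a recorded answer.

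As a minor correction, change item 9 to 33 mL for adults and 23 mL for children.

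The cost is one added question and one corrected line on a form that is still a draft, with its OMB number left as a placeholder.
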